## **4.3 Randomization**

Randomization will be performed using a 3:1 allocation ratio using a block size of 4 separately in each cohort.

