### **2. STUDY PLAN**

#### **2.1 Study Design**

This is a randomized, open-label phase II study designed to evaluate the safety and efficacy of etoposide in patients with COVID-19 infection. Treatment will be comprised of etoposide administered intravenously at a dose of 150 mg/m^2 on Days 1 and 4 in patients with COVID-19 infection meeting eligibility criteria. Subsequent doses of etoposide will be allowed if the investigator and treating physician believe the patient had clinical benefit from etoposide therapy but subsequently has evidence of recurrent clinical deterioration.

Two cohorts of patients will be treated with etoposide. Cohort 1 will be patients who require intubation due to their severe COVID-19 related respiratory illness. Cohort 2 will be COVID-19 patients who have progressive pulmonary dysfunction and evidence of severe inflammation but who are not yet intubated. Although prior treatment for COVID with anti-cytokine therapy will not exclude a patient from enrollment on this trial, a “washout” period of at least 3 half-lives will be required prior to initiation of etoposide therapy. Enrollment will begin with cohort 1, following which a decision will be made to open cohort 2 or not, as outlined further in this document.

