## **2.2 Number of sites**

One (Boston Medical Center, [name])

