## **2.3 Number of patients**

- 32 patients in each cohort with 3:1 allocation ratio (24 etoposide and 8 control per cohort)
- 64 patients total

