# **3. PARTICIPANT SELECTION**

## **3.1 Screening, Recruitment, and Consenting**

The investigators will recruit participants from within Boston Medical Center on the inpatient setting. It will be standard for COVID-19 positive patients to be screened to determine if they may be eligible for any available clinical trials. A screening consent is not obtained, as the pre-screening review is conducted prior to contacting the patient to discuss the trial. At that time no data will be collected by the study team. The medical records are reviewed to determine if a patient may or may not be potentially eligible for a clinical trial.

If the patient is potentially eligible, the inpatient nurse, treating physician or trial representative will inform the patient or the patient's legally authorized representative (LAR) of the availability of a clinical trial. No research procedures are performed until after written consent is obtained.

If the patient agrees to discuss and receive information about the study, a copy of the IRB-approved Informed Consent Form will be provided to the patient by a member of the patient's clinical care team to avoid using additional personal protective equipment (PPE). In the event the

patient is too ill to make medical decisions, the patient's LAR will be asked to review the informed consent form, which may be sent electronically.

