The inpatient provider will contact the research nurse and provide the phone number of the patient or the LAR. The research nurse and/or investigator will call the patient or the LAR and will remotely conduct the consent discussion, reviewing all elements of consent and emphasizing the voluntary nature of research participation. Additional family members or friends may join the call at the subject's request. Once all questions have been asked and answered to the patient's/LAR's satisfaction, the research nurse will offer to end the call so the patient/LAR can be given the opportunity to review the consent form and discuss with family members (remotely) and/or other physicians. The patient/LAR will have as long to decide as possible within the confines of the clinical urgency. Once the patient/LAR is satisfied that all questions have been answered, if he/she wishes to participate, he/she will contact the research nurse or the research nurse will reach out to the patient/LAR again if requested by the patient/LAR. The study team will have arranged for a witness to join the telephone call at this point, and consent will be obtained remotely, with the patient or LAR directing the witness to sign on their behalf. The informed consent will also be documented in the medical record.

The study team member conducting the consent discussion and the witness will both sign and date the consent form external to the patient's room. The signed consent form will be filed in the research records. The patient will keep the unsigned copy.

Potential participants who are non-English speaking will be consented using the Short Form (if IRB approved). A hospital interpreter, or an interpreter on the phone line, will be used throughout the consent process and throughout their participation in the study. The interpreter will sign as an impartial witness.

Documentation that informed consent occurred prior to the subject's entry into the study and the informed consent process will be recorded in the subject's source documents.

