## **4. INVESTIGATIONAL PLAN**

### **4.1 Overall Design**

Open-label, randomized Phase II study of etoposide administered intravenously at a dose of 150 mg/m^2 once daily on Days 1 and 4 for a total of two doses to inpatient patients with moderate and severe COVID-19 who have consented to treatment on this clinical trial. Dose reductions will be performed as outlined in Section 5.

This study includes a screening period, a treatment period, and a follow-up period for adverse events that will include the remainder of hospitalization, with additional assessments at days 30 and 60 as outlined in the study calendar (Section 6). After obtaining informed consent, the patients randomized to etoposide will begin treatment with the study drug. Subjects randomized to control will receive standard of care treatment. No placebo will be used. Subjects will be monitored for adverse events and to evaluate study outcomes. Patients removed from the study due to any unacceptable adverse events will also be followed until time of death or hospital discharge.

For patients randomized to standard of care, day 1 will be considered day of randomization. These patients will be followed to record the outcome of all primary and secondary objectives until time of death or hospital discharge, whichever occurs earlier.

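### A single fixed block of 4 at 3:1, written in the protocol of an open-label single-site trial, makes an expected 43.75% of allocations deducible in advance

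*Combined protocol and SAP*

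**What the plan says.** Section 4.3 is one sentence: "Randomization will be performed using a 3:1 allocation ratio using a block size of 4 separately in each cohort". Section 2.3 gives the resulting numbers, which are 32 patients per cohort, 24 on etoposide and 8 on control.

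The surrounding design lets past assignments be seen. Section 2.1 states "This is a randomized, open-label phase II study", Section 4.1 adds "No placebo will be used", and Section 2.2 names one site.

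On recruitment, Section 3.1 says "The investigators will recruit participants from within Boston Medical Center on the inpatient setting" and "The research nurse and/or investigator will call the patient or the LAR and will remotely conduct the consent discussion". One exclusion criterion in Section 3.3 rests on the investigator's opinion, and Section 10.1 makes the investigator the assessor of the primary endpoint.

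The documents do not say who generates or holds the allocation list. They describe neither varying block sizes nor any step that keeps the block size from those who recruit.

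**The concern.** A 3:1 block of 4 holds exactly one control. Once that control has appeared, every later allocation in the block must be etoposide. If the first three are etoposide, the fourth must be control. Concealing the list does not prevent this, because the next assignment follows from the earlier ones and the earlier ones are visible.

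Blocking separately by cohort does not hide the sequence either. Cohort is defined by intubation status, and each cohort's count starts at a block boundary.

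What is at stake is the comparability of the arms. A recruiter who knows what the next patient will receive can, deliberately or not, let that influence whom to approach, when to approach them, or how to apply a discretionary exclusion. The intention-to-treat analysis in Section 7.2 does not correct this, because the selection would happen before randomization. Section 7.1 offers the trial as initial evidence of efficacy, and that reading depends on comparable arms.

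**Working it through.** **Inputs.** Block size 4 and ratio 3:1 (Section 4.3); 32 patients per cohort, 24 and 8 (Section 2.3); Fisher's exact test for the primary endpoint (Section 7.2).

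**The plan's own figure.** 32/4 = 8 complete blocks, and 8 × 3 = 24 etoposide and 8 × 1 = 8 control. This reproduces Section 2.3. The documents give no figure for predictability.

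**Certain allocations per block.** The control is equally likely to be in each of the four positions.

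| Position of control | Later allocations certain | Of which etoposide | Of which control |
|---|---|---|---|
| 1 | 3 | 3 | 0 |
| 2 | 2 | 2 | 0 |
| 3 | 1 | 1 | 0 |
| 4 | 1 | 0 | 1 |
| Mean | 7/4 = 1.75 | 6/4 = 1.5 | 1/4 = 0.25 |

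The closed form agrees. With e etoposide and c control allocations per block, the expected number certain is e/(c+1) + c/(e+1) = 3/2 + 1/4 = 1.75. As a share, 1.75/4 = 43.75%.

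**Per cohort of 32 (8 blocks).** 8 × 1.75 = 14 expected certain allocations: 8 × 1.5 = 12 of the 24 etoposide (50%) and 8 × 0.25 = 2 of the 8 control (25%). The possible range is 8 × 1 = 8 to 8 × 3 = 24. Position 4 is certain in every block. Until the control appears, its probability at positions 1 to 4 is 1/4, 1/3, 1/2 and 1, so there is partial information beyond the certain cases.

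**Sensitivity of the result to single controls.** One control patient is 1/8 = 12.5 percentage points. For illustration, with two-sided Fisher's exact test, 19/24 v 4/8 gives p = 0.18 and 19/24 v 2/8 gives p = 0.010. These counts are hypothetical. They show how much two control outcomes weigh, not what steering would achieve.

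**Alternatives.** The same closed form for a fixed block of 8 (e = 6, c = 2) gives 6/3 + 2/7 = 2.286, and 2.286/8 = 28.6%. For blocks of 4 and 8 in random order, simulation with an observer who knows both sizes and sees every assignment gives:
- about 10% certain if the list is cut at 32 wherever the block ends;
- about 15% certain (about 14.5% with 20,000 cohorts) if the blocks are fitted to exactly 32 and the observer uses that total.

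**The case against.** The strongest reply is that 43.75% overstates what a recruiter gains. At 3:1, always guessing etoposide is right 75% of the time. With blocks of 4, the best guess is right 13/16 = 81.25% of the time, a gain of 6.25 points. Most of the certain allocations (12 of 14) are to etoposide, and only 2 of 8 controls are foreseeable. This is correct and limits the size of the point. It does not remove it: certainty is more usable than a good guess, and knowing that the next patient will receive etoposide is enough to influence whom to approach.

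Second, most eligibility criteria are numeric thresholds, and clinical urgency limits the time to decide, so there is little room for steering. Section 3.1 also bars research procedures before written consent, which arguably already places allocation after consent. This narrows the risk, but the investigator-opinion exclusion remains, and confirmed eligibility before release is not stated.

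Third, small blocks protect the ratio at an early look, and Section 7.1 says that the trial is not powered to detect a statistically significant difference. The first part is a real trade-off and is costed with the fix. The second lowers the stakes but does not make comparability of the arms unimportant.

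A reader might go further and infer that 44% of allocations were known to staff, that the block size was public during recruitment, or that enrolment was steered. The documents support none of these. The share is knowable only to someone who tracks assignments and block starts, and nothing says that anyone did. The documents do not say when the protocol became public; the point needs only that the recruiting investigators hold it.

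**Conclusion.** The point holds as a foreseeable and unguarded risk of selection bias that is cheap to reduce. Its size is the expected 14 deducible allocations per cohort, split 12 etoposide and 2 control. It assumes complete blocks that start at the first patient of each cohort, and an observer who knows the block size and sees every earlier assignment in that cohort.

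No effect on the response rates or on the type I error has been shown, and none can be derived from the documents. The concealment procedure may be set out in a separate manual, but concealing the list alone would not cure predictability from a known block size. The change should be made, but the weakness does not by itself invalidate the comparison.

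**What to change.** In Section 4.3, replace the single block size with permuted blocks of randomly varying size (for example 4 and 8, both compatible with 3:1), separately by cohort. Keep the sizes out of the protocol and away from recruiting staff, in a document held by whoever generates the list. State that each allocation is released only after consent and eligibility are confirmed.

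The cost is a new list and a sentence or two of text. Balance becomes slightly looser at the interim after 10 patients (Sections 4.2 and 9.4). Fixed blocks of 4 guarantee 2 or 3 controls among the first 10, while mixed blocks of 4 and 8 allow 1 to 4. That look already falls mid-block under the present plan, since 10 is not a multiple of 4. Balance is also looser if a cohort stops mid-block.

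The sponsor should choose how the list ends. Fitting the blocks to exactly 32 keeps the 24:8 split but leaves about 15% of allocations deducible. Cutting the list at 32 lowers this to about 10%, but if a block of 8 begins after patient 28 the control count can be 7 to 9, because its first four places can hold 0 to 2 controls.

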## **4.4 Schema**

Etoposide 150 mg/m^2 administered intravenously once daily on Days 1 and 4. If the treating clinicians feel that the patient initially benefited from etoposide but then has evidence of relapse of cytokine storm, the patient may continue on the standard HLH-94 etoposide schedule of day 8, 11, 18, 25 after discussion with one of the study investigators (prior to day 8 dosing).

## **4.5 Criteria for removal from protocol treatment**

- Completion of study (either death or completion of day 60 survival assessment)
- Unacceptable toxicity
- Participant withdrawal for any reason

## **5. DRUG FORMULATION AND ADMINISTRATION**

### **5.1 Etoposide Chemistry, Mechanism of Action, and Formulation**

Chemistry: Etoposide is a semi-synthetic podophyllotoxin derivative from the plant *podophyllum peltatum*, and has antineoplastic properties in experimental animals and in man.

Mechanism of action: The epipodophyllotoxins exert specific spindle poison activity with metaphase arrest, but in contrast to the vinca-alkaloids, have an additional activity of inhibiting

cells from entering mitosis. Suppression of tritiated thymidine, uridine, and leucine incorporation in human cells in tissue culture suggests effects against DNA, RNA and protein synthesis.

Formulation: 100mg of VP-16 is supplied as 5ml or 10ml solution in sterile multiple dose vials for injection. The pH of the yellow clear solution is 3-4. Each ml contains 20mg VP-16, 2mg citric acid, 30mg of benzyl alcohol, 80mg polysorbate 80/tween 80, 650mg polyethylene glycol 300, and 30.5% (v/v) alcohol. VP-16 must be diluted prior to use with either 5% Dextrose Injection, USP, or 0.9% sodium chloride injection, USP. The time before precipitation occurs depends on concentration, however when at a concentration of 0.2mg/ml it is stable for 96 hours at room temperature and at 0.4mg/ml it is stable for 48 hours. Concentrations over 0.5mg/ml is stable for at least 24 hours at room temperature.

## **5.2 Etoposide Availability**

Etoposide is commercially available.

## **5.3 Etoposide Administration**

Etoposide 150 mg/m^2 will be administered over 60 minutes intravenously on Days 1 and 4. Admixed in NS-500ml.

If the treating clinicians feel that the patient initially benefited from etoposide but then has evidence of relapse of cytokine storm, the patient may continue on the standard HLH etoposide schedule of day 8, 11, 18, 25 after discussion with one of the study investigators.

## **5.4 Etoposide Expected Toxicities and Management**

Reversible myelotoxicity has been uniformly observed to be the major toxicity for VP-16 and to represent the only clinically significant side effect. Following a single IV injection, peak myelotoxicity occurs at seven to nine days. Following daily injections for five to seven days, myelotoxicity is maximal between 12-16 days from the initiation of therapy. Bone marrow suppression is mainly manifested as granulocytopenia, with thrombocytopenia and anemia occurring to a lesser extent. Gastrointestinal toxicities including transient modest nausea, vomiting, and diarrhea, are common. Other reactions could include aftertaste, rash, pigmentation, pruritis, abdominal pain, constipation, and dysphagia. Occasional alopecia is reported. VP-16 does not produce phlebitis or nephrotoxicity. Rarely anaphylactic-like reactions have been reported, as well as, hypotension. The drug is to be infused over 60 minutes in this study to decrease the potential for hypotension, and the blood pressure and pulse will be monitored during the infusion. Occasionally, chills, fever, peripheral neurotoxicity, stomatitis, hepatotoxicity, transient cortical blindness and radiation recall dermatitis may be a result of VP-16 administration. Stomatitis is usually associated with high dose regimens containing etoposide. The occurrence of acute leukemia has been reported rarely in patients treated with VP-16 in association with other antineoplastic agents. Etoposide can cause fetal harm when administered to a pregnant women. It has been shown to be teratogenic in mice and rats. In females of reproductive potential, etoposide may cause infertility and result in amenorrhea. Premature menopause can occur with etoposide. Recovery of menses and ovulation is related to

age at treatment. Males In male patients, etoposide may result in oligospermia, azoospermia, and permanent loss of fertility. Sperm counts have been reported to return to normal levels in some men, and in some cases, have occurred several years after the end of therapy Secondary leukemias associated with etoposide have been reported. Women of childbearing potential will be advised to avoid becoming pregnant for at least 6 months after the final dose of etoposide. Males with female partners of reproductive potential will be advised to use effective contraception for 4 months after the final etoposide dose.

Safety of etoposide for use by nursing women has not been established.

## 5.5 Etoposide Dose Modifications

### Etoposide dosing in Hepatic and Renal Insufficiency

T. Bili 1.5 – 3.0 mg/dL	50% dose reduction
T. Bili > 3.0 mg/dL	Omit dose
AST > 2.5 x ULN	50% dose reduction
Albumin < 3.0 g/dL	30% dose reduction
Creatinine Clearance 15-50 mL/min*	25% dose reduction
Creatinine Clearance <15 mL/min	Omit dose
Abs Neutrophil Count <500/uL	Hold until ANC > 500/uL

\*calculated by Cockcroft Gault equation

## 5.6 Etoposide Drug Interactions

Patients receiving concomitant medications with known interactions with etoposide, as mentioned below, will be monitored closely for adverse events.

- Cisplatin: Co-administration of cisplatin may increase exposure to etoposide.
- Highly protein-bound drugs: Phenylbutazone, sodium salicylate, and aspirin displaced protein-bound etoposide in vitro.
- Select antiepileptic medications: Co-administration with antiepileptic medications including phenytoin, phenobarbital, carbamazepine, and valproic acid may increase etoposide clearance.
- Etoposide may be a substrate of the P-glycoprotein (P-gp) transporter system based upon in vitro studies

Co-administration of etoposide with warfarin may result in elevated international normalized ratio (INR). If patients taking warfarin the INR will be monitored at least twice weekly.

## 6. STUDY PROCEDURES & CALENDAR

REQUIRED STUDIES	Screening	Day 1, Day 4 and Day 7 Σ#	Prior to discharge	Day 30*
PHYSICAL				
History & Physical Exam	X	X	X	X
Height, Weight, Body Mass Index, and Body Surface Area	X			
Vital Signs	X	X	X	X
Toxicity Notation	X	X	X	X
Respiratory Status on 8 point scale ^	X	X	X	X
HISTORY				
Concomitant medicines (including COVID therapies, ie hydroxychloroquine, tocilizumab, anakinra) with date of initiation	X			
Smoking status	X			
Comorbidities	X			
Symptoms, including date of symptom onset	X			
LABORATORY				
Beta HCG (for women of childbearing potential)	X			
CBC with Differential +	X	X	X	X
Comprehensive metabolic panel +	X	X	X	X
Lactate Dehydrogenase	X	X	X	X
D-dimer	X	X	X	X
Ferritin	X	X	X	X
C-reactive protein	X	X	X	X
PaO 2 /FIO 2 (P/F) ratio (cohort 2 only)	X	X	X	X
INR (if on warfarin) Ω	X			
ADDITIONAL TESTING				
Electrocardiogram (ECG)	X			

# For subjects randomized to treatment, the data for Day 1 and Day 4 will be collected prior to the etoposide dose (within 24 hours).

\*Information to be obtained as feasible, if patient has been discharged attempts will be made to obtain the information from the patient's primary care provider. If such results are not available, participant will be contacted by the research nurse to assess toxicities.

^ Mortality assessment (included on the 8 point scale) will also be recorded at Day 14 and 60, in addition to Day 30 mentioned above

+ CBC and comprehensive metabolic panel will be measured at least twice weekly during hospitalization. These tests will also be obtained pre-dose 8, 11, 18, and 25 for those patients who require additional etoposide dosing as described above (Section 4.3 and 5.3)

Ω INR to be repeated at least twice weekly for patients on warfarin

Σ Day 1 of treatment for patients randomized to standard of care (SOC) will be considered the day of randomization

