## **2.5 Secondary Objectives**

- Overall Survival at 30 days is a key secondary endpoint.
- Improvement in inflammatory markers associated with cytokine storm (Ferritin, C-Reactive Protein (CRP), d-dimer, white blood cell count)
- Cumulative incidence of grade 3 and 4 adverse events during hospitalization
- Cumulative incidence of serious adverse events during hospitalization
- Duration of hospitalization
- Duration of ventilation
- Ventilator free days (reintubations or death within 28 days will result in zero ascribed time off ventilator prior to reintubation)
- Improvement in oxygenation or paO2/FIO2 ratio

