### **3.2 Inclusion Criteria (applicable for patients enrolled for treatment or data collection)**

- Age 18 years or older
- Confirmed COVID-19 infection
- Evidence of cytokine storm defined as:
  - Peak ferritin > 10,000 ng/mL OR
  - Peak ferritin > 500 ng/mL and one or more of the following at any time during hospital admission:
    - Lactate dehydrogenase > 500 U/L, d-dimer > 1000 ng/mL, C-reactive protein > 100 mg/L, or WBC > 15 k/uL
- Cohort 1: Intubated status as a result of COVID infection-associated respiratory illness
- Cohort 2 (if activated): Evidence of progressive respiratory failure (requiring >4 L/min of supplemental oxygen to maintain SaO2 greater than 92%) without intubation

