## 7.2 Statistical Analysis

Tabulations overall, and by treatment group, will be produced for appropriate demographic, baseline, efficacy, and safety parameters, with number and percentages reported for categorical variables and the mean, median, standard deviation, and range for continuous variables. All analyses will be performed at an  $\alpha=0.05$  level using SAS v.4.

Efficacy analyses will be performed in an intention-to-treat (ITT) population consisting of all patients randomized. The difference in ordinal scale improvement rates between treatment arms will be calculated with a 95% confidence interval and formally compared using Fisher's Exact Test. For secondary analysis of the primary endpoint, logistic models individually adjusted for age, diabetes, chronic lung disease/moderate or severe asthma, immunocompromise, liver disease, heart disease/hypertension, smoking and obesity (BMI  $> 40$ ), residence in long-term care facility, will also be examined with odds ratios and 95% confidence intervals reported.

The analysis of secondary time to event endpoints including survival at 30 days, duration of hospitalization, duration of ventilation and ventilator free days, will be compared between treatment arms based on a log-rank test. The median will be estimated with a 95% CI for each treatment arm using the Kaplan-Meier method. Cox proportional Hazards models adjusted individually for age, diabetes, chronic lung disease/moderate or severe asthma, immunocompromise, liver disease, heart disease/hypertension, smoking and obesity (BMI  $> 40$ ), residence in long-term care facility, will also be examined with odds ratios and 95% confidence intervals reported. Changes in inflammatory markers and in oxygenation or  $\text{paO}_2/\text{FIO}_2$  ratio, based on available recorded measurements, will be compared between treatment arms using a two sample t-test, or a Wilcoxon Rank Sum test, as appropriate. Incidence of grade 3 or 4 AEs and serious AEs will be compared using Fisher's Exact test.

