## 8.2 Response Definitions

8-Point Ordinal Scale:

- 8 - Death;
- 7 - Ventilation in addition to extracorporeal membrane oxygen (ECMO), continuous renal replacement therapy (CRRT), or need for vasopressors (dopamine  $\geq 5$   $\mu$ g/kg/min OR epinephrine  $\geq 0.1$   $\mu$ g/kg/min OR norepinephrine  $\geq 0.1$   $\mu$ g/kg/min);
- 6 - Intubation and mechanical ventilation;
- 5 - Non-invasive mechanical ventilation (NIV) or high-flow oxygen;
- 4 - Hospitalized, requiring oxygen by mask or nasal prongs;
- 3 - Hospitalization without oxygen supplementation;
- 2 - Discharged from hospital either to home with supplemental oxygen OR to inpatient rehabilitation/skilled nursing facility (+/- supplemental oxygen);
- 1 - Discharged to home without supplemental oxygen

When calculating Ventilator Free days, reintubations or re-hospitalizations or death occurring in the first 28 days should result in zero ascribed to time off the ventilator prior to reintubation

When calculating days of hospitalization, re-hospitalization or death occurring in the first 28 days should result in zero ascribed to time out of the hospital prior to readmission.

When determining days of supplemental oxygen use and need for supplemental oxygen, the patient will only be considered to no longer need supplemental oxygen if a room air saturation is  $\geq 90\%$  after five minutes of rest.

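### In cohort 2 the oxygenation endpoint rests on a P/F ratio with no FiO2 rule for mask or nasal oxygen and no rule for patients who die or go home

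*Combined protocol and SAP*

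**What the plan says.** - **Objective (Section 2.5).** The last of eight secondary objectives is "Improvement in oxygenation or paO 2 /FIO 2 ratio". The word oxygenation is not defined further, and the objective is not limited to one cohort.
- **Population (Section 3.2).** Cohort 2 enters on "Evidence of progressive respiratory failure (requiring >4 L/min of supplemental oxygen to maintain SaO 2 greater than 92%) without intubation". Oxygen need is expressed as a flow, with no upper limit short of intubation.
- **Respiratory support (Section 8.2).** Category 4 is mask or nasal-prong oxygen in hospital. Category 5 is "Non-invasive mechanical ventilation (NIV) or high-flow oxygen". Both can occur in cohort 2.
- **Schedule (Section 6).** Under the column head "REQUIRED STUDIES", the row "PaO 2 /FIO 2 (P/F) ratio (cohort 2 only" is marked at screening, Days 1, 4 and 7, before discharge and at Day 30. There is no separate arterial-gas row, no rule for deriving FiO2 and no substitute if no arterial sample is drawn. Vital signs are marked at the same visits, but saturation is not named among them.
- **Day 30 (Section 6 footnote).** "Information to be obtained as feasible, if patient has been discharged attempts will be made" through the primary care provider. Failing that, a research nurse contacts the participant about toxicities.
- **Analysis (Section 7.2).** Changes in oxygenation or the ratio, "based on available recorded measurements, will be compared between treatment arms using a two sample t-test, or a Wilcoxon Rank Sum test, as appropriate". The same section sets the efficacy population as everyone randomized. For this endpoint it gives no time point, no missing-data rule and no rule for deaths.
- **Size (Section 2.3).** "32 patients in each cohort with 3:1 allocation ratio (24 etoposide and 8 control per cohort".

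**The concern.** Both parts of the ratio, and the set of patients it is compared in, are left open.

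- **Denominator.** On mask or nasal-prong oxygen the inspired fraction depends on device, flow and breathing, and someone has to estimate it. Without a fixed rule, two assessors can give the same patient different ratios. A patient who moves between categories 5 and 4 also switches from a set to an estimated FiO2, so a change of device can look like a change in the lung. The trial is open-label, so there is no safeguard against the estimate being influenced by knowledge of the arm.
- **Numerator.** Every value needs an arterial sample, including in patients weaned to room air and in outpatients at Day 30.
- **Who is compared.** With no rule for deaths or discharge, the worst and the best outcomes can both be missing from the comparison, at rates that may differ by arm.

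At stake is whether the oxygenation result in cohort 2 can be read alongside the primary result. There are only 8 planned controls, so little loss is affordable.

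**Working it through.** The plan states no SD, effect size, power or expected availability for the ratio, so it has no figure of its own to reproduce. Step 1 uses only the text. Steps 2 to 4 are illustrations under stated assumptions.

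**1. Who can supply a value at each visit (Section 6 against Sections 7.2 and 8.2)**

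- Screening: all patients are in hospital and the row is required.
- Days 1 and 4: required for every patient still in hospital.
- Day 7: a patient who has died has no value. A patient already discharged has at most a pre-discharge value, and the plan does not say whether that stands in.
- Before discharge: only patients who leave alive, at differing times.
- Day 30: patients still in hospital can supply a value. Discharged patients (categories 1 and 2, the best end of the scale) do so only if outside results exist, and the fallback contact about toxicities cannot yield an arterial ratio. Patients who have died have none.

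From Day 7 onwards, having a value therefore depends on outcome, and Section 7.2 has no rule to offset this.

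**2. Denominator (assumed PaO2 70 mmHg; assumed FiO2 0.30 to 0.50 for one mid-range flow)**

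P/F = PaO2 / FiO2. 70/0.30 = 233 and 70/0.50 = 140. The ratio of the two is 233/140 = 1.7, with no change in the patient.

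Put another way, with log-normal error in FiO2 a true ratio of 150 is recorded within 150 × exp(±1.96s). That is 123 to 182 for s = 0.10, 101 to 222 for s = 0.20 and 83 to 270 for s = 0.30.

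**3. Availability (if recording depended on outcome)**

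Improvement rates of 80% and 30% are borrowed from Section 7.1, where they are Day 14 assumptions for the primary endpoint. The recording probabilities q are pure assumptions. Measured fraction = r·q(improved) + (1 − r)·q(unimproved).

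| q improved / unimproved | Etoposide, of 24 | Control, of 8 | Improved among measured | Difference |
|---|---|---|---|---|
| complete | 24 | 8 | 80% vs 30% | 50 points |
| 0.2 / 0.8 | 0.16 + 0.16 = 0.32, 7.7 | 0.06 + 0.56 = 0.62, 5.0 | 50% vs 10% | 40 points |
| 0.1 / 0.9 | 0.08 + 0.18 = 0.26, 6.2 | 0.03 + 0.63 = 0.66, 5.3 | 31% vs 5% | 26 points |

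**4. Precision (if values were lost at random)**

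Detectable standardized difference d, two-sided 0.05, 80% power, noncentral t with n1 + n2 − 2 degrees of freedom and noncentrality d·√(n1·n2/(n1 + n2)):

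- 8 vs 24 (complete): 1.18 SD
- 6 vs 18 (75%): 1.38 SD
- 4 vs 12 (50%): 1.74 SD
- 2 vs 6 (25%): 2.75 SD

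**The case against.** The strongest reply is that the calendar already answers much of this.

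- **The ratio is a required study.** It is marked at every listed visit for all cohort 2 patients, and that row is itself the arterial schedule. A reader might infer that the ratio will exist only in patients who worsen. The documents do not support that: it forecasts non-adherence and does not describe the plan. What stands is that Section 7.2 accepts whatever was recorded, that the Day 30 provision is loose, and that deaths and discharges remove values even with perfect adherence.
- **FiO2 is often known.** It is normally set on non-invasive ventilation, on high-flow oxygen and after later intubation, and it is 0.21 on room air. A reader might infer that the endpoint is mostly imprecise or unusable in cohort 2. The documents do not say how many patients will be on mask or nasal oxygen, so that is not supported. The gap is confined to those patients and to moves between devices.
- **Another measure is allowed.** The objective permits oxygenation as an alternative to the ratio. This helps little: the term is undefined, and the ratio is the only explicit oxygenation row in the calendar.
- **The figures are illustrative.** This is correct. The planned test compares changes in the ratio, not the share improved among those measured, and the improvement rates come from a day with no scheduled ratio. In both illustrations the difference keeps its direction, so they do not show that the endpoint is uninformative.
- **SpO2/FiO2 uses the same denominator.** Also correct. The fixed conversion table addresses the denominator; saturation addresses only the need for arterial sampling.

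**Conclusion.** The concern holds in limited form. In cohort 2 the plan relies on an arterial P/F ratio, gives no FiO2 rule for mask or nasal-prong oxygen, and compares the values that happen to exist, with no time point and no rule for deaths or early discharge. From Day 7 onwards the compared set depends on outcome, even if the calendar is followed in full.

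The size cannot be derived from the documents. The 1.7-fold spread rests on an assumed FiO2 range, and the fall from 50 to 40 or 26 points rests on assumed recording probabilities. The direction of bias is also open: the illustrations shrink the difference, but dropping deaths would flatter whichever arm had more of them.

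Severity is low to moderate. This is one of eight secondary objectives, in a cohort that opens only if permitted (Section 4.2), in a study that describes itself as not powered for a significant difference (Section 7.1).

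**What to change.** In Sections 6 and 7.2, for cohort 2 patients who are not intubated:

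1. Name SpO2 explicitly within the vital signs already scheduled at each visit, and record oxygen device and flow with it.
2. Derive SpO2/FiO2 with one fixed device-and-flow conversion table, using 0.21 on room air and the set FiO2 where a device sets it. Apply the same FiO2 rule to any P/F reported.
3. Compare Day 7, the last fixed-day visit before Day 30, between arms in all randomized cohort 2 patients by the Wilcoxon rank-sum test that Section 7.2 already allows. Rank deaths worst. State a rule for patients discharged before Day 7, for example use of their scheduled pre-discharge reading. State also that patients intubated by Day 7 stay in, with the ventilator FiO2.
4. Keep arterial P/F as supplementary.

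**Cost.** Calendar and analysis wording, plus two recorded items per saturation; the endpoint would depend less on arterial sampling. SpO2/FiO2 is less sensitive near full saturation. Because oxygen is adjusted to hold saturation, it largely reflects the FiO2 needed. The table applies one FiO2 rule in both arms but does not remove the error.
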